4. SECONDARY AND EXPLORATORY OBJECTIVES

- CLL/MCL cohort (Cohort A)
 - To increase the incidence of successful outcome (defined as lack of requirement of second line therapy for acute GVHD, lack of NIH severe chronic GVHD, lack of progression or relapse of CLL/MCL, lack of death from disease or non-relapse causes) to at least 60% at 1 year post HCT.

- To study the safety and tolerability of ibrutinib post HCT in patients with non-Hodgkin lymphoma (NHL) and HL (cohort A and B combined)
- Acute GVHD
 - To study the incidence of grade 3-4 acute GVHD in the first 6 months post HCT in patients with NHL and HL (cohort A and B combined)
 - To study the incidence of second line therapy (systemic only) for acute GVHD in the first 6 months post HCT in patients with NHL and HL (cohort A and B combined)
 - To study the incidence of recurrent acute GVHD in the first 6 months post HCT in patients with NHL and HL (cohort A and B combined)
- Chronic GVHD
 - To study the incidence and severity of chronic GVHD in the first 12 months post HCT in patients with NHL and HL (cohort A and B combined)
 - To study the incidence of lung involvement with GVHD in the first 12 months post HCT in patients with NHL and HL (cohort A and B combined)
 - To study the incidence of sclerotic skin chronic GVHD in the first 12 months post HCT in patients with NHL and HL (cohort A and B combined)
- To study the incidence of infectious deaths not related to GVHD in patients with non-Hodgkin and Hodgkin lymphoma (cohort A and B combined)
- Correlative studies
 - Cohort A: To study the association of MRD as detected by IgH sequencing prior to starting ibrutinib and compare to post ibrutinib at month 6, 9 and 12 after HCT. In addition to study the impact of onset of new acute or chronic GVHD on MRD.
 - Cohort A: To study the association of T-cell clonality by T cell receptor (TCR) Vb sequencing prior to starting ibrutinib and compare to post ibrutinib at month 6, 9 and 12 after HCT. In addition to study the impact of onset of new acute or chronic GVHD on TCR sequencing.
 - Cohort A: To study the association of B cell receptor signaling pathways and immune function with response by single cell mass cytometry prior to starting ibrutinib and compare to post ibrutinib at month 6, 9 and 12 after HCT.
 - Cohort A: To study the association of single cell mass cytometry that investigates B cell receptor signaling and its association with new acute or chronic GVHD on BCR signaling.

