5.3 Rationale for Duration of Ibrutinib Post HCT

Although the incidence of complete response (CR) in MCL and CLL in the non-transplant population is low^{1;4-6}, the incidence of CR post HCT is higher. Also, it is expected that GVT will be the final pathway to effect cure. The role of ibrutinib post HCT is to maintain effective tumor control until GVT is established. In the absence of clinical GVHD, immunosuppressive therapy (IST) is tapered starting at day 100, with a goal of IST cessation by 6 months post HCT. Thus, stopping ibrutinib at 12 months post HCT in patients who have achieved a CR reflects a time point at which one would expect GVT to be established. Also, it is expected that ibrutinib may down modulate chronic GVHD. It is not clear if ibrutinib can facilitate transplantation tolerance. We hypothesize that using ibrutinib starting at day 60-90 post HCT until 12 months post HCT, will increase the incidence of a successful outcome by 25% compared to historical controls. The correlative studies will address molecular monitoring of disease (in cohort A), mechanisms of relapse of disease and development (or lack of) GVHD.

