6.5 Dose and Administration

Ibrutinib will be administered at a dose of 420 mg by mouth once a day starting between day 60-90 post HCT and continue until 1y post HCT. Ibrutinib is dispensed as 140 mg capsules and patients will be

instructed to take 3 capsules by mouth once a day. Patients will be instructed to take the drug at approximately the same time every day. Patients will be instructed to swallow the capsules whole with water and not to open, break or chew the capsules.

If a dose of ibrutinib is not taken at the scheduled time, it can be taken as soon as possible on the same day with a return to the normal schedule the following day. Extra capsules of ibrutinib should not be taken to make up for the missed dose.

For patients on azoles, the starting dose will be 140 mg by mouth once a day starting between day 60-90 post HCT and continue until 1y post HCT.

Patients using Posaconazole as outlined in section 11.2 will start ibrutinib at a dose of 70 mg by mouth once a day between day 60-90 post HCT and continue until 1 year post HCT.

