- Standard of care: Following should be done **weekly for 4 weeks and then monthly until 6 months post HCT and then at month 9** after starting ibrutinib
 - Hematology
 - Hematology parameters performed at local laboratory will include at a minimum a complete blood count: white blood cells, red blood cells, hemoglobin, hematocrit, platelets, and absolute neutrophil count.
 - Chemistry
 - Serum chemistry parameters performed at local laboratory will include at a minimum: creatinine, AST, ALT, alkaline phosphatase, and total bilirubin.

- Standard of care: To be done at month 6 and 9 post-HCT Peripheral blood T-cell, B-cell and NK cell subsets (CD3+, CD4+, CD8+, CD19+, CD16/56+)
- Research: Following should be done **at month 6 and 9 after** starting ibrutinib
 - A peripheral blood sample on all patients should be sent for Immunoseq for T-cell receptor. See the Laboratory Manual for sample acquisition, processing and shipping logistics.
 - Research: a peripheral blood sample will be collected for CyTOF analyses. See the Laboratory Manual for detailed instruction on collection, processing and shipping.
- Toxicity assessment:
 - Research: Toxicity assessment will be done on first day of administration of ibrutinib to establish post-HCT baseline.
 - Research: Toxicity assessment will be done weekly after the start of ibrutinib until day 100 post HCT or at least 4 weeks post-ibrutinib (whichever is longer)
 - Research: Toxicity assessment will be done monthly until 12 months post HCT. Month 7,8, 10, and 11 toxicity assessment can be done telephonically if a patient is unable to travel back to the transplant center. A final toxicity assessment will be conducted 12 months post HCT.
 - Concomitant medication use will be recorded at month 6 and month 9
- Acute GVHD assessment
 - Standard of care: weekly assessment of acute GVHD until day 100 (+/- 1 week) post HCT or at least 4 weeks post-ibrutinib (whichever is longer). See the Clinical Assessment Manual for acute GVHD assessment forms
- Chronic GVHD assessment
 - Standard of care: Assessment at month 6 and 9 post HCT. NIH 2015 diagnosis and scoring forms will be used. See the Clinical Assessment Manual for chronic GVHD assessment forms

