At the time of new diagnosis of acute or chronic GVHD (from start of ibrutinib until 1 y post-HCT)

- Standard of care: Assessment of acute GVHD (See the Clinical Assessment Manual if applicable.)
- Standard of care: Assessment of chronic GVHD (See the Clinical Assessment Manual if applicable.)
- Research: Peripheral blood samples on all patients (cohort A only) should be sent for IMMUNOSEQ for T-cell receptor and for immunoseqMRD analysis if a new diagnosis of acute or chronic GVHD is made and ideally before starting new therapy. This may happen in between the

planned assessment time points. See the Laboratory Manual for collection, processing and shipping details.

- Research: peripheral blood sample on all patients (cohort A only) should be sent for CyTOF analyses if a new diagnosis of acute or chronic GVHD is made and ideally before starting new therapy. This may happen in between the planned assessment time points. See the Laboratory Manual for collection, processing and shipping details.

12 Months post HCT or earlier if withdrawing from the study (including withdrawal prior to initiation of Ibrutinib)

- Standard of care:
 - History and physical, KPS (see the Clinical Assessment Manual)
 - Hematology
 - Hematology parameters performed at local laboratory will include at a minimum a complete blood count: white blood cells, red blood cells, hemoglobin, hematocrit, platelets, and absolute neutrophil count.
 - Chemistry
 - Serum chemistry parameters performed at local laboratory will include at a minimum: creatinine, AST, ALT, alkaline phosphatase, and total bilirubin
 - Quantitative immunoglobulins including IgG, IgM and IgA
 - Peripheral blood T-cell, B-cell and NK cell subsets (CD3+, CD4+, CD8+, CD19+, CD16/56+)
 - Assessment of acute GVHD (see the Clinical Assessment Manual) if applicable
 - Assessment of chronic GVHD (see the Clinical Assessment Manual) if applicable. NIH 2015 diagnosis and scoring forms will be used.
 - Disease reassessment has to be done for end of study only if prior disease assessment is more than 4 weeks prior to end of study. Disease reassessment will include: appropriate imaging (CT scan and/or PET scan or other imaging) as clinically indicated and bone marrow biopsy. PB should be sent for chimerism analyses. Ablative transplants will require only % recipient vs. donor. RIC HCT will require sorted chimerisms (CD 3: % recipient vs. donor and CD33 or lineage specific marker: % recipient vs. donor)
- Research:

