12. Weekly assessment of acute GVHD: post-ibrutinib, weekly for 4 weeks or until day 100 post HCT whichever is later. See the Clinical Assessment Manual.
13. Please ensure eligibility checklist is complete and has been reviewed by coordinating center prior to the administration of ibrutinib between day 60 and 90 post HCT. All SOC and research studies must be done within 2 weeks of starting ibrutinib.
14. Toxicity assessment should be at the transplant center 30 days after cessation of study drug in addition to end of study.
15. The End of Study visit should be completed even for patients who withdraw from study without initiating Ibrutinib

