24.3 Safety Analyses

HCT is a complex procedure with varying causes of death post HCT. Patients may die of relapse or progression of disease, development or worsening of acute GVHD after exposure to study drug, development or worsening of chronic GVHD after exposure to study drug, infections in absence of GVHD or other causes (other non-relapse mortality) (includes drug adverse effects).

Both cohort A and B will be at risk for these events and thus will be included in the safety analyses.

In order to safeguard patients, we have set the following limits:

- Development of grade 3-4 acute GVHD by day 180 post HCT for patients who have no acute GVHD prior to starting experimental therapy should not be higher than 30%.
- Development of grade 3-4 acute GVHD for patients with grade 1-2 acute GVHD prior to starting experimental therapy should not be higher than 40%.
- Development of grade 3-4 acute GVHD for patients with any grade acute GVHD prior to starting experimental therapy should not be higher than 50%.
- Cumulative incidence of infectious disease mortality (not related to GVHD) should not be higher than 30% at 1 y post HCT
- Cumulative incidence of non-relapse mortality (all cause) at 1 y post HCT should not be higher than 40%

Stopping Rules

Cohort B is an exploratory cohort of 10 patients with diagnoses of follicular lymphoma or Hodgkin disease. Combining cohort, A and B with 75 patients in total, the stopping rules are created based on Bayesian approach to monitor treatment related AEs defined below during the conduct of a clinical trial. We will stop the trial early if the probability that treatment related events of the current regimen exceeds conventional treatment related AE is greater than 80%.

The following tables describe the safety rules. There will be 2 conference calls per month during the conduct of the study to ensure the implementation of the safety rules.

Development of grade 3-4 acute GVHD by day 180 post HCT for patients who have no acute GVHD prior to starting experimental therapy should not be higher than 30%.

Number of patients in complete cohorts of 5 (inclusive)	Stop the trial if this number of toxicities (inclusive)
5	3
10	5
15	7
20	8
25	10
30	12

Development of grade 3-4 acute GVHD for patients with grade 1-2 acute GVHD prior to starting experimental therapy should not be higher than 40%.

Number of patients in complete cohorts of 5 (inclusive)	Stop the trial if this number of toxicities (inclusive)
5	4
10	6
15	8
20	10

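### Scheduled acute GVHD grading ends at day 100-118, while the acute GVHD objectives run to 6 months and the first stopping rule to day 180

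*Combined protocol and SAP*

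**What the plan says.** **Assessment schedule.** Footnote 12 of the Cohort A study table (section 22.1) says: "Weekly assessment of acute GVHD: post-ibrutinib, weekly for 4 weeks or until day 100 post HCT whichever is later". Footnote 11 of the Cohort B table (section 22.2) gives the same rule. Section 20 has "weekly assessment of acute GVHD until day 100 (+/- 1 week) post HCT or at least 4 weeks post-ibrutinib", taking the longer of the two. Under section 6.5 ibrutinib is given "once a day starting between day 60-90 post HCT". After weekly grading ends, the tables list acute GVHD assessment in only two places: the column for a new GVHD diagnosis, which section 20 heads "At the time of new diagnosis of acute or chronic GVHD", and the 12-month or end-of-study visit.

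**Objectives.** Section 4 sets three acute GVHD objectives for both cohorts combined, all over the first 6 months: grade 3-4 disease, second-line systemic therapy, and recurrence ("To study the incidence of recurrent acute GVHD in the first 6 months post HCT").

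**Stopping rules.** Section 24.3 has three acute GVHD rules.
- The first covers patients with no acute GVHD before ibrutinib and runs to day 180, with a 30% limit.
- The second is "Development of grade 3-4 acute GVHD for patients with grade 1-2 acute GVHD prior to starting experimental therapy should not be higher than 40" per cent.
- The third covers patients with acute GVHD of any grade before ibrutinib, with a 50% limit.

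The second and third state no time window.

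**The concern.** An incidence over a fixed window needs the event to be looked for throughout that window, in the same way for every patient. Here weekly grading stops well before the window closes, and the next scheduled grading comes about six months after it has closed. What remains is an event-driven assessment, and its wording fits only part of what has to be counted. Recurrent GVHD follows earlier GVHD by definition. The second and third stopping rules concern patients who already had acute GVHD and then reach grade 3-4. Neither is clearly a new diagnosis.

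At stake are three secondary endpoints and the numerators of three safety rules. A grade 3-4 event that is not recorded as such lowers the count set against the boundary, so any error from this source points towards continuing the trial.

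**Working it through.** The plan gives no figure for this gap, so there is none to reproduce. The check is date arithmetic followed by a comparison of triggers.

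**1. Length of the gap.** Inputs: start day 60 to 90 (section 6.5); end of weekly grading at the later of day 100 and start + 28 (footnotes and section 20); end of window at day 180 (first stopping rule, and assumed here to equal 6 months for the objectives).

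End = max(100, start + 28). Gap = 180 - end.

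| Start day | End of grading | Gap (days) | Gap / 180 | Gap / (180 - start) | Gap if +1 week is used |
|---|---|---|---|---|---|
| 60 | 100 | 80 | 44.4% | 80/120 = 66.7% | 73 |
| 72 | 100 | 80 | 44.4% | 80/108 = 74.1% | 73 |
| 80 | 108 | 72 | 40.0% | 72/100 = 72.0% | 65 |
| 90 | 118 | 62 | 34.4% | 62/90 = 68.9% | 55 |

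The share of the time from first dose to day 180 peaks at a day-72 start, the last day for which day 100 still governs. Its range is 67-74%. Using the +1 week window moves the end of grading to day 107-125.

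**2. What triggers an assessment inside the gap.**

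| Event in the gap | Counted in | New diagnosis? |
|---|---|---|
| First onset, no earlier acute GVHD | Rule 1; grade 3-4 objective | Yes: assessment triggered |
| Low-grade onset on ibrutinib, later worsening to grade 3-4 | Rule 1; grade 3-4 objective | Onset yes; worsening not clearly |
| GVHD present before ibrutinib, worsening to grade 3-4 | Rules 2 and 3; grade 3-4 objective | Not clearly |
| Recurrence after earlier GVHD | Recurrence objective | Not clearly |

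**3. How sensitive a stopping rule is to missed events (illustration only).** The first rule stops at 3/5, 5/10, 7/15, 8/20, 10/25 or 12/30. Let p be the true grade 3-4 rate and m the share of all such events not recorded. Each group of five patients adds a Binomial(5, p(1 - m)) count, and the trial stops at the first look where the total reaches the boundary. The documents give neither p nor m; both are assumed. Exact probabilities of stopping by 30 patients:

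| p | m = 0 | m = 10% | m = 20% | m = 30% |
|---|---|---|---|---|
| 40% | 0.74 | 0.60 | 0.44 | 0.30 |
| 45% | 0.87 | 0.76 | 0.60 | 0.42 |

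This shows that the rule is sensitive to incomplete counts. It does not estimate how incomplete they would be. Because a first onset does trigger assessment, m under rule 1 could be small.

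**The case against.** The strongest reply is that severe worsening would come to light anyway. Section 20 keeps history and physical monthly to month 6, monthly toxicity assessment, a chronic GVHD assessment at month 6 and concomitant medication recording at month 6. Section 25 counts exacerbations of pre-existing conditions as adverse events and requires hospitalizations to be reported as serious events within 24 hours. Section 11.1 requires GVHD to be ruled out in persistent severe gastrointestinal toxicity. Section 24.3 provides two safety calls a month. This stands to a large extent. A reader might infer that worsening in the gap goes uncaptured, or that the endpoints will certainly be under-counted, and the documents support neither. For second-line therapy in particular, the month-6 medication record falls at the end of the window, and the Cohort B table lists concomitant medications in the monthly column without restriction. What remains is that none of these routes is stated to include acute GVHD grading. Adverse events are graded by CTCAE, whereas acute GVHD has its own assessment forms.

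A second reply is that the table column is headed as monthly unless stated otherwise, so monthly grading might be the default once weekly grading ends. The footnote does state its own end, however, and the laboratory rows in the same column spell out a monthly continuation to month 6 that the acute GVHD row lacks.

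A third is that the Clinical Assessment Manual, cited in the footnotes, may schedule later grading. It is not among the documents, so this cannot be excluded; if it does, the protocol text needs to be brought into line.

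Two further inferences should be avoided. The two-thirds figure is a share of the time from first dose to day 180, not of all time on ibrutinib, which continues to 1 year. And although section 5.3 says "immunosuppressive therapy (IST) is tapered starting at day 100", that sentence is limited to patients without clinical GVHD. It does not show that the gap coincides with a taper in patients who already have GVHD. Section 5.4 describes a typical taper after day 100 more generally.

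**Conclusion.** The mismatch is real and can be read directly from the protocol: 62 to 80 days without scheduled acute GVHD grading (55 to 73 with the +1 week window) before the 6-month and day-180 windows close. That is 34-44% of the 180 days after transplant and 67-74% of the time from first dose to day 180. Recurrence, worsening of GVHD present before ibrutinib, and worsening after a low-grade onset on ibrutinib are not clearly graded in that stretch. Rules 2 and 3 are exposed too, though with no stated window their gap cannot be measured.

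The direction of any bias is towards fewer recorded events and fewer boundary crossings. Its size is unknown, since indirect capture exists and the missed share is not given. The conclusion rests on 6 months meaning day 180, on the footnote being the operative schedule, and on a new diagnosis not covering recurrence or worsening. Confidence is moderate because the Clinical Assessment Manual could not be seen. This is a cheap improvement, not a flaw that undermines the trial.

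**What to change.** In both cohort tables and in section 20, add acute GVHD grade and any second-line systemic therapy for acute GVHD to the monthly history-and-physical visits already scheduled to month 6. Reword the trigger for the clinical acute GVHD assessment to cover new, recurrent or worsened acute GVHD. Leave the Cohort A research blood draws tied to a new diagnosis: the same trigger now orders the TCR, MRD and CyTOF samples, so widening it wholesale would add draws. Check the Clinical Assessment Manual for any later grading schedule and make the texts agree.

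The cost is one more form at existing visits and slightly more data entry, plus a clinical assessment when GVHD recurs or worsens. No scheduled visit, research sample or treatment changes.

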22.2 Cohort B

Assessment	Within 4 weeks prior to starting preparative regimen for HCT	Start of Prep until day +60 post-HCT (± 1 week)	Day +60 to Day +90 & prior to administration of ibrutinib ¹² (± 1 week)	Post-ibrutinib monthly assessment unless stated otherwise (start of ibrutinib until 1 y post HCT) (± 1 week)	At time of suspected relapse/ progression (start of ibrutinib until 1 y post HCT)	At time of new dx of acute or chronic GVHD (start of ibrutinib until 1 yr post HCT)	12M post HCT or EOS (± 2 weeks) ¹⁴	30 Day Follow Up (+ 7 days)
History and Physical Exam	X	X	X	X (monthly until M6, then M9)			X	
KPS (see the Clinical Assessment Manual)	X	X (q2 weeks)	X (q2 weeks)	X (monthly until M6, then M9 post-SCT)			X	
Transplant evaluation per institutional criteria	X ¹							
Hematology labs	X		X	X (weekly for 4 weeks and then monthly until M6, then M9)			X	
Chemistry labs	X		X	X (weekly for 4 weeks and then monthly until M6, then M9)			X	
Coagulation studies	X		X					
Hepatitis serology	X							
Pregnancy test (for WOCBP)	X		X					
EKG	X		X					
Echocardiogram	X							
PFT	X							
IgG, IgA, IgM	X						X	
Peripheral blood T and B cell subsets	X			X (M6, M9 post-HCT)			X	
Disease assessment	X ¹	X ³		X (M6, M9 post-HCT)	X		X ⁹	
DNA banking for subsequent chimerism analyses	X ¹							
Chimersim analyses		X		X (M6, M9 post-HCT)	X		X ⁹	
Bone marrow biopsy	X	X			X			

Assessment	Within 4 weeks prior to starting preparative regimen for HCT	Start of Prep until day +60 post-HCT (± 1 week)	Day +60 to Day +90 & prior to administration of ibrutinib ¹² (± 1 week)	Post-ibrutinib monthly assessment unless stated otherwise (start of ibrutinib until 1 y post HCT) (± 1 week)	At time of suspected relapse/ progression (start of ibrutinib until 1 y post HCT)	At time of new dx of acute or chronic GVHD (start of ibrutinib until 1 yr post HCT)	12M post HCT or EOS (± 2 weeks) ¹⁴	30 Day Follow Up (+ 7 days)
Acute GVHD assessment		X ⁵	X ⁵	X ¹¹		X	X	
Chronic GVHD assessment		X ⁶ (monthly)	X ⁶ (monthly)	X (M6, M9 post-SCT)		X	X	
Study drug (ibrutinib)			Start between day 60-90 post HCT until 12 months post HCT					
Con meds	X	X	X	X			X	
Ibrutinib toxicity assessment	X	X	X	X ⁸ (weekly for first 4 weeks then monthly until M11)			X ¹³	X ¹³

Between month 12 and month 24: patients will be followed for chronic GVHD, disease status and survival. See section on HCT outcome between 1y and 2y.

Red font is research

1. Transplant evaluation timing is per institutional criteria and does not have to be within 4 weeks of starting HCT
2. Peripheral blood sample for CyTOF analyses. Research sample. See the Laboratory Manual for sample acquisition, processing and shipping logistics
3. Disease reassessment should be done between day 30 and day 60 post-HCT. Imaging (CT scan and/or PET scan or other imaging) as clinically indicated
4. BM biopsy for disease assessment is considered standard of care.
5. Weekly assessment of acute GVHD ± 3 days. Assessment of acute GVHD may start after engraftment. See the Clinical Assessment Manual.
6. Assessment of chronic GVHD should occur monthly (± 1 week) post-transplant. See the Clinical Assessment Manual.
7. Peripheral blood sample for IMMUNOSEQ analyses for T-cell receptor assay (TCR) and for immunoseqMRD analyses. Research sample. See the Laboratory Manual for sample acquisition, processing and shipping logistics
8. Ibrutinib toxicity assessment. Weekly toxicity assessment for first 4 weeks after starting ibrutinib. Subsequently toxicity assessment should be monthly until month 11 post SCT. Toxicity assessment at month 7,8, 10, 11 can be done over the phone if patient is unable to travel to the transplant center. All other time points for toxicity assessment should be done at the transplant center.
9. Disease reassessment needs to be done at end of study, only if previous disease assessment has been done more than 4 weeks prior to end of study.
10. Diagnostic sample from disease onset (paraffin block of lymph node only) if available must be sent for immunoseqMRD analyses. See the Laboratory Manual for sample acquisition, processing and shipping logistics.
11. Weekly assessment of acute GVHD: post-ibrutinib, weekly for 4 weeks or until day 100 post HCT whichever is later. See the Clinical Assessment Manual.

12. Please ensure eligibility checklist is complete and has been reviewed by coordinating center prior to the administration of ibrutinib between day 60 and 90 post HCT. All SOC and research studies should be done within 2 weeks of starting ibrutinib.
13. Toxicity assessment should be at the transplant center 30 days after cessation of study drug in addition to end of study
14. The End of Study visit should be completed even for patients who withdraw from study without initiating Ibrutinib

